8.2.8 Discontinuation of study

Novartis reserves the right to discontinue any study under the conditions specified in the clinical trial agreement.

8.3 Ethics and Good Clinical Practice

This study must be carried out in compliance with the protocol and in accordance with Novartis standard operating procedures. These are designed to ensure adherence to Good Clinical Practice, as described in:

1. ICH Harmonized Tripartite Guidelines for Good Clinical Practice 1996. Directive 91/507/EEC, The Rules Governing Medicinal Products in the European Community.
2. US 21 Code of Federal Regulations dealing with clinical studies (including parts 50 and 56 concerning informed consent and IRB regulations).
3. Declaration of Helsinki, concerning medical research in humans (Recommendations Guiding Physicians in Biomedical Research Involving Human Subjects, Helsinki 1964, amended Tokyo 1975, Venice 1983, Hong Kong 1989, Somerset West 1996).

The investigator agrees, when signing the protocol, to adhere to the instructions and procedures described in it and thereby to adhere to the principles of Good Clinical Practice that it conforms to.

8.3.1 Institutional Review Board/Independent Ethics Committee

Before implementing this study, the protocol, the proposed informed consent form and other information to subjects, must be reviewed by a properly constituted Institutional Review Board/Independent Ethics Committee (IRB/IEC/REB). A signed and dated statement that the protocol and informed consent have been approved by the IRB/IEC/REB must be given to Novartis before study initiation. The name and occupation of the chairman and the members of the IRB/IEC/REB must be supplied to Novartis. Any amendments to the protocol, other than administrative ones, must be approved by this committee.

8.3.2 Informed consent

The investigator must explain to each subject (or legally authorized representative) the nature of the study, its purpose, the procedures involved, the expected duration, the potential risks and benefits involved and any discomfort it may entail. Each subject must be informed that participation in the study is voluntary and that he/she may withdraw from the study at any time and that withdrawal of consent will not affect his/her subsequent medical treatment or relationship with the treating physician.

This informed consent should be given by means of a standard written statement, written in non-technical language. The subject should read and consider the statement before signing and dating it, and should be given a copy of the signed document. If written consent is not possible, oral consent can be obtained if witnessed by a signed statement from one or more persons not involved in the study, mentioning why the patient was unable to sign the form. No patient can enter the study before his/her informed consent has been obtained.

The informed consent form is considered to be part of the protocol, and must be submitted by the investigator with it for IRB/IEC/REB approval. Novartis supplies a proposed informed consent form, which complies with regulatory requirements and is considered appropriate for the study. Any changes to the proposed consent form suggested by the Investigator must be agreed to by Novartis before submission to the IRB/IEC/REB, and a copy of the approved version must be provided to the Novartis monitor after IRB/IEC/REB approval.

8.3.3 Declaration of Helsinki

The investigator must conduct the trial in accordance with the Declaration of Helsinki. A copy of the Declaration of Helsinki is provided in the investigator folder at each site.

World Medical Association Declaration of Helsinki: Recommendations Guiding Medical Doctors in Biomedical Research Involving Human Subjects.

Adopted by the 18th World Medical Assembly, Helsinki, Finland, 1964 and as revised by the World Medical Assembly in Tokyo, Japan in 1975, in Venice, Italy in 1983, in Hong Kong in 1989 and the 48th General Assembly in Somerset West, Republic of South Africa, 1996.

Introduction

It is the mission of the physician to safeguard the health of the people. His or her knowledge and conscience are dedicated to the fulfillment of this mission.

The Declaration of Geneva of the World Medical Association binds the physician with the words, "The health of my patient will be my first consideration," and the International Code of Medical Ethics declares that, "A physician shall act only in the patient's interest when providing medical care which might have the effect of weakening the physical and mental condition of the patient."

The Purpose of biomedical research involving human subjects must be to improve diagnostic, therapeutic and prophylactic procedures and the understanding of the etiology and pathogenesis of disease.

In current medical practice most diagnostic, therapeutic or prophylactic procedures involve hazards. This applies especially to biomedical research.

Medical progress is based on research which ultimately must rest in part on experimentation involving human subjects.

In the field of biomedical research a fundamental distinction must be recognized between medical research in which the aim is essentially diagnostic or therapeutic for a patient, and medical research, the essential object of which is purely scientific and without implying direct diagnostic or therapeutic value to the person subjected to the research.

Special caution must be exercised in the conduct of research which may affect the environment, and the welfare of animals used for research must be respected.

Because it is essential that the results of laboratory experiments be applied to human beings to further scientific knowledge and to help suffering humanity, the World Medical Association has prepared the following recommendations as a guide to every physician in biomedical research involving human subjects. They should be kept under review in the future. It must be stressed that the standards as drafted are only a guide to physicians all over the world. Physicians are not relieved from criminal, civil and ethical responsibilities under the laws of their own countries.

I. Basic Principles

Biomedical research involving human subjects must conform to generally accepted scientific principles and should be based on adequately performed laboratory and animal experimentation and on a thorough knowledge of the scientific literature.

The design and performance of each experimental procedure involving human subjects should be clearly formulated in an experimental protocol which should be transmitted for consideration, comment and guidance to a specially appointed committee independent of the investigator and the sponsor provided that this independent committee is in conformity with the laws and regulations of the country in which the research experiment is performed.

Biomedical research involving human subjects should be conducted only by scientifically qualified persons and under the supervision of a clinically competent medical person. The responsibility for the human subject must always rest with a medically qualified person and never rest on the subject of the research, even though the subject has given his or her consent.

Biomedical research involving human subjects cannot legitimately be carried out unless the importance of the objective is in proportion to the inherent risk to the subject.

Every biomedical research project involving human subjects should be preceded by careful assessment of predictable risks in comparison with foreseeable benefits to the subject or to others. Concern for the interests of the subject must always prevail over the interests of science and society.

The right of the research subject to safeguard his or her integrity must always be respected. Every precaution should be taken to respect the privacy of the subject and to minimize the impact of the study on the subject's physical and mental integrity and on the personality of the subject.

Physicians should abstain from engaging in research projects involving human subjects unless they are satisfied that the hazards involved are believed to be predictable. Physicians should cease any investigation if the hazards are found to outweigh the potential benefits.

In publication of the results of his or her research, the physician is obliged to preserve the accuracy of the results. Reports of experimentation not in accordance with the principles laid down in this Declaration should not be accepted for publication.

In any research on human beings, each potential subject must be adequately informed of the aims, methods, anticipated benefits and potential hazards of the study and the discomfort it may entail. He or she should be informed that he or she is at liberty to abstain from participation in the study and that he or she is free to withdraw his or her consent to participation at any time. The physician should then obtain the subject's freely-given informed consent, preferably in writing.

When obtaining informed consent for the research project the physician should be particularly cautious if the subject is in a dependent relationship to him or her or may consent under duress. In that case the informed consent should be obtained by a physician who is not engaged in the investigation and who is completely independent of this official relationship.

In case of legal incompetence, informed consent should be obtained from the legal guardian in accordance with national legislation. Where physical or mental incapacity makes it impossible to obtain informed consent, or when the subject is a minor, permission from the responsible relative replaces that of the subject in accordance with national legislation. Whenever the minor child is in fact able to give a consent, the minor's consent must be obtained in addition to the consent of the minor's legal guardian.

The research protocol should always contain a statement of the ethical considerations involved and should indicate that the principles enunciated in the present Declaration are complied with.

II. Medical Research Combined with Professional Care (Clinical Research)

In the treatment of the sick person, the physician must be free to use a new diagnostic and therapeutic measure, if in his or her judgment it offers hope of saving life, reestablishing health or alleviating suffering.

The potential benefits, hazards and discomfort of a new method should be weighed against the advantages of the best current diagnostic and therapeutic methods.

In any medical study, every patient--including those of a control group, if any--should be assured of the best proven diagnostic and therapeutic method. This does not exclude the use of inert placebo in studies where no proven diagnostic or therapeutic method exists.

The refusal of the patient to participate in a study must never interfere with the physician-patient relationship.

If the physician considers it essential not to obtain informed consent, the specific reasons for this proposal should be stated in the experimental protocol for transmission to the independent committee (I,2).

The physician can combine medical research with professional care, the objective being the acquisition of new medical knowledge, only to the extent that medical research is justified by its potential diagnostic or therapeutic value for the patient.

III. Non-Therapeutic Biomedical Research Involving Human Subjects (Non-Clinical Biomedical Research)

In the purely scientific application of medical research carried out on a human being, it is the duty of the physician to remain the protector of the life and health of that person on whom biomedical research is being carried out.

The subjects should be volunteers--either healthy persons or patients for whom the experimental design is not related to the patient's illness.

The investigator or the investigating team should discontinue the research if in his/her or their judgment it may, if continued, be harmful to the individual.

In research on man, the interest of science and society should never take precedence over considerations related to the well-being of the subject.

8.4 Preserving confidentiality of pharmacogenetic data

The preservation of confidentiality of pharmacogenetic data is also detailed in the Substudy 1 Protocol for countries where this assessment is required to be separate from the core protocol.

To protect the research subject against the risk of loss of confidentiality, all DNA samples will be marked with a unique code number and all genetic assay results will have a different unique bar code from the DNA. This information is stored in an anonymous fashion in two different secured computer databases, one containing the DNA sample codes and the other with the genetic information to maximize confidentiality.

Results of these studies are for research purposes only and since they are not expected to benefit the subject directly or to alter their treatment course, these results will not be placed in their medical record and will not be made available to the subject, members of their family, their personal physician, or other third parties except as specified below.

Unless required by law or regulatory authorities for the purpose of verifying information obtained from this study, only Novartis Pharmaceuticals Corporation (the sponsor) and its authorized personnel and agents will have access to the confidential genetic data. Novartis will not collect or maintain data which identifies the subject by name. The investigator will collect and maintain that information. The results and other information from this study may be submitted to the FDA and governmental agencies in other countries where the Study Drugs may be considered for approval; however, the subject will be identified by initials and subject study number only. The lead investigators for this study may have access to the bar-coded genetic information for purposes of data analysis and publication. Individual subjects will not be identified in any reports or publications resulting from this study. Because of the need to give these parties access to this information, absolute confidentiality cannot be guaranteed.

Appendix 2: Study Diary

Novartis PHARMACEUTICALS CORPORATION: Blood Sugar Testing Diary PLEASE RETURN THIS DIARY TO THE CLINIC ON YOUR NEXT SCHEDULED VISIT DATE Study : CDJN608 B2302																		
Subject Initials _____		Issued Visit: _____			Next Visit : _____													
Center :				Subject:					Issue date:					Next Visit date:				
										day	mont	year				day	mo	yea
										h				nth	r			
Blood Sugar Testing Diary																		
OCCURRENCES OF SUSPECTED HYPOGLYCEMIA (LOW BLOOD SUGAR)																		
List Symptoms (include duration)	Surrounding Circumstances	Date Day/month/ year	Time of Day	Blood Sugar Test Result	Time of Last Meal	Date of Last Dose day/month/ year	Time of Last Dose	Type of Treatmen t	Time to Recovery									
		/ /	AM _____ PM _____	Not done Yes _____	AM _____ PM _____	/ /	AM _____ PM _____											
		/ /	AM _____ PM _____	Not done Yes _____	AM _____ PM _____	/ /	AM _____ PM _____											
		/ /	AM _____ PM _____	Not done Yes _____	AM _____ PM _____	/ /	AM _____ PM _____											
		/ /	AM _____ PM _____	Not done Yes _____	AM _____ PM _____	/ /	AM _____ PM _____											

The actual diary will have extra rows to record suspected hypoglycemia events.
At every visit a sheet will be distributed for each week between visits.

Appendix 3: Notable ranges for selected laboratory tests and measurements of vital signs

Results that meet the below mentioned criteria need to be commented on by the investigator on the CRF.

Laboratory notable range criteria:

Laboratory variables:	Notable Abnormalities	
	Standard Units	SI Units
HEMATOLOGY		
Hemoglobin	≤ 11.5 (m), 9.5 (f) g/d	≤ 7.1 (m), 5.9 (f) mmol/l
Hematocrit	≤ 37 (m), 32(f) %	≤ 37 (m), 32 (f) %
Erythrocytes	≤ 4 (m), 3.5 (f) 10 ⁶ /mm ³ ≥ 7 (m), 6.5 (f) 10 ⁶ /mm ³	≤ 4 (m), 3.5 (f) 10 ¹² /L ≥ 7 (m), 6.5 (f) 10 ¹² /L
Leukocytes	≤ 2.8 ≥ 16 10 ³ mm ³	≤ 2.8 ≥ 16 10 ⁹ /l
BIOCHEMISTRY		
Alkaline Phosphatase	≥ 3 x ULN	≥ 3 x ULN
ALT (SGPT)	≥ 3 x ULN	≥ 3 x ULN
AST (SGOT)	≥ 3 x ULN	≥ 3 x ULN
BUN	≥ 40 mg/dl	≥ 14.2 mmol/l
Creatinine	> 2.5 mg/dl	> 221 μmol/l
Fasting Plasma Glucose	≤ 45 or ≥ 250 mg/dl	≤ 2.5 or ≥ 13.2 mmol/l
Potassium	≤ 3.0 or ≥ 6.0 mEq/l	≤ 3.0 or ≥ 6.0 mmol/l
Sodium	≤ 115 or ≥ 160 mEq/l	≤ 115 or ≥ 160 mmol/l
Total Cholesterol	≥ 350 mg/dl	≥ 9.1 mmol/l

m = male f = female

Vital signs notable range criteria:

Vital Signs		Notable Abnormalities or Change Since the Previous Visit
Pulse (beats per minute)		< 40 or > 160 or increase/decrease > 50 since the previous visit
Blood Pressure (mmHg)	Systolic	< 60 or > 210 or increase/decrease > 50 since the previous visit
	Diastolic	< 40 or > 130 or increase/decrease > 30 since the previous visit
Weight (kg)		< 30 or > 220 or increase/decrease > 10% since the previous visit

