3.5.3 Efficacy assessment

Efficacy assessments will be performed at every visit following randomization.

Primary endpoint: time to progression to diabetes (V1, N1)

In order to assess patients' diabetic condition the following procedure must be followed: When a patient has an FPG \geq 126 mg/dL (7.0 mmol/L) or a 2hr post-challenge glucose \geq 200 mg/dL (11.1 mmol/L) during the trial, a repeat OGTT should be performed as soon as possible (on a different day), preferably within 4 weeks (28 days) but not later than 12 weeks (84 days) after the day of the initial laboratory assessment indicative of diabetes. If, for whatever reason, a repeat OGTT cannot be performed, at least an FPG should be performed at that time.

The progression to diabetes endpoint is defined through (a) an algorithm based on central laboratory measurements of FPG and/or 2hr OGTT, or (b) adjudication by the Diabetes Endpoint Adjudication Committee as follows:

1. Endpoint definition based on laboratory tests: FPG \geq 126 mg/dL (7.0 mmol/L) or a 2hr post-challenge glucose (OGTT) \geq 200 mg/dL (11.1 mmol/L) during two consecutive valid measurements that are within 12 weeks (\leq 84 days) but at least one day apart. The time to progression to diabetes is defined as the time of the original measurement (subsequently confirmed) of an FPG \geq 126 mg/dL (7.0 mmol/L) or a 2hr post-challenge glucose \geq 200 mg/dL (11.1 mmol/L).
2. Adjudication by the Diabetes Endpoint Adjudication Committee: progression to diabetes may be confirmed by the Committee in cases suggestive of diabetes but where above laboratory test-based definition does not hold (e.g. due to missing central laboratory measurements or repeat tests outside the 12-week time limit). E.g., the Committee will adjudicate cases where diabetes has been diagnosed by a primary care physician (possibly based on local laboratory assessments) and/or where anti-diabetic medication has been initiated; adjudication also includes deciding on the time to progression to diabetes. Details of adjudication are provided in a Diabetes Endpoint Adjudication Charter to be followed by the Committee.

An HbA_{1c} measurement cannot replace an FPG or a 2hr post-challenge glucose to confirm progression to diabetes.

Primary endpoint: extended CV endpoint (V2, N2)

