The central (or local) laboratory will use standardized normal value ranges, utilize the same methods and references for methodology and will supply the sponsor with their internal quality control methods and external evaluations of methods and certification.

Laboratory results will be forwarded to the investigator and sponsor for review. The investigator should retain all laboratory results in the patient's source documents.

Notable ranges for selected laboratory tests are provided in Appendix 3.

Hematology

Includes hematocrit, hemoglobin, platelet count, erythrocyte count, total leukocyte count. These parameters will be measured Visit 1 (one measurement must be available prior to randomization), annually thereafter and at the final visit.

Blood chemistry

A fasting venous blood sample will be obtained for analysis of creatinine, SGOT (ALT), SGPT (AST), alkaline phosphatase, LDH, triglycerides, total cholesterol, potassium, sodium, calcium, chloride, BUN, total protein. All tests will be measured at Visit 1 (one measurement must be available prior to randomization), annually thereafter and at the final visit with the exception of LDL and HDL cholesterol which will be measured at Visit 1, Visit 11 (Month 36) and at the final visit, only.

Creatinine and potassium should be measured in patients already receiving an ACE inhibitor or who are initiated on an ACE inhibitor during the course of the study. Creatinine and potassium levels will be assessed at the local laboratory during the initial titration phase at Visit 3 (Week 2) and 4 (Week 4), and after 2 weeks of exposure to the higher dose in the event the patient has his/her initial titration after Visit 3.

Fasting Plasma Glucose (FPG)

FPG will be measured at Visit 1 and at the final visit, respectively (as part of OGTT), and semi-annually from visit 6-11. Thereafter FPG will be measured annually (as part of OGTT).

For patients who have progressed to diabetes and have had an FPG \geq 300 mg/dL (16.7 mmol/L), an annual OGTT is no longer required; an FPG, however, should still be performed. An annual OGTT is still required for all patients with FPG < 300 mg/dL (16.7 mmol/L).

HbA_{1c}

Blood samples for HbA_{1c} will be collected at baseline (visit 2) and at the final study visit. In addition, HbA_{1c} will be measured in subjects with positive, confirmatory OGTT and annually thereafter in patients who have progressed to diabetes.

Urine measurements

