6.1.6 Safety evaluation

The assessment of safety will be based mainly on the frequency of all adverse events and on the number of laboratory values that fall outside of pre-determined ranges. Other safety data (e.g. electrocardiogram, vital signs, special tests) will be considered as appropriate.

Adverse events will be summarized by presenting, for each treatment group, the number and percentage of patients having any adverse event, having an adverse event in each body system and having each individual adverse event. Any other information collected (e.g. severity or relatedness to study medication) will be listed as appropriate.

For the subset of patients at prospectively defined study centers who will be dispensed glucometers, the number and percentage with confirmed hypoglycemic events (plasma glucose < 3.3 mmol/l) will be presented. The number and percentage of patients with any events suggestive of hypoglycemia will also be presented for this subset, in order to be able to put the number of confirmed vs. suggestive events into a perspective. Patients who were dispensed glucometers at the investigator's discretion (i.e. not from the pre-defined centers) will not be shown in this summary.

Laboratory data will be summarized by presenting shift tables using extended normal ranges (baseline to most extreme post-baseline value), by presenting summary statistics of raw data and change from baseline values (means, medians, standard deviations, ranges) and by the flagging of notable values in data listings.

Data from other tests (e.g. electrocardiogram or vital signs) will be listed, notable values will be flagged, and any other information collected will be listed as appropriate.

Unless otherwise indicated, the safety population will be used for the safety analyses.

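### The two upper notable limits for fasting plasma glucose in Appendix 3 do not convert: 250 mg/dL is 13.9 mmol/L, and the stated 13.2 mmol/L is about 238 mg/dL

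*Protocol*

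**What the plan says.** Appendix 3 sets out notable laboratory abnormalities in two parallel columns, standard units and SI units. For fasting plasma glucose the entries are "≤ 45 or ≥ 250 mg/dl" and "≤ 2.5 or ≥ 13.2 mmol/l". The layout presents these as one criterion in two unit systems.

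The appendix attaches a duty to the table: "Results that meet the below mentioned criteria need to be commented on by the investigator on the CRF". Section 3.5.4 (Laboratory evaluations) refers readers to Appendix 3 for these ranges. Section 6.1.6 (Safety evaluation) gives notable values one further use. Among the ways of presenting laboratory data, it lists summarising "by the flagging of notable values in data listings".

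Elsewhere the protocol gives several glucose thresholds in both units. Section 3.5.3 pairs 126 mg/dL with 7.0 mmol/L and 200 mg/dL with 11.1 mmol/L. Section 3.5.4 pairs 300 mg/dL with 16.7 mmol/L. Section 3.3.2 pairs 140 mg/dL with 7.8 mmol/L.

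**The concern.** A limit printed in two units should classify a given result the same way in both. The upper FPG limit does not. A patient with an FPG of 240 mg/dL (13.3 mmol/L) meets the criterion in the SI column and misses it in the standard-unit column.

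The limit is not just background text. It decides which results the investigator has to comment on, and which results carry a flag in the safety listings. As printed, both outcomes for values in the gap turn on the column used and not on the patient's glucose. High FPG values are of obvious interest in a trial of progression to diabetes. FPG also continues to be measured after a patient has progressed, so values in this range can be expected to occur.

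**Working it through.** **Inputs, all from the protocol**

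- Notable FPG limits, standard units: 45 and 250 mg/dL (Appendix 3).
- Notable FPG limits, SI units: 2.5 and 13.2 mmol/L (Appendix 3).
- Other glucose pairs, used to fix the conversion factor (Sections 3.3.2, 3.5.3 and 3.5.4).

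**Step 1. The protocol's own conversion factor** (mg/dL divided by mmol/L)

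| Pair | Implied factor |
|---|---|
| 126 / 7.0 | 18.00 |
| 200 / 11.1 | 18.02 |
| 140 / 7.8 | 17.95 |
| 300 / 16.7 | 17.96 |
| 45 / 2.5 (lower notable limit) | 18.00 |
| 60 / 3.3 (confirmed hypoglycemia) | 18.18 |
| **250 / 13.2 (upper notable limit)** | **18.94** |

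All pairs except the last agree with a factor of 18 to one decimal place. The small departures, such as 18.18 for 60/3.3, come from rounding.

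**Step 2. Convert the two notable limits**

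- Lower: 45 / 18 = 2.50 mmol/L. The stated 2.5 is reproduced.
- Upper: 250 / 18 = 13.89 mmol/L, which rounds to 13.9. The stated 13.2 is not reproduced.
- Reverse: 13.2 × 18 = 237.6 mg/dL, about 238.

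With a factor of 18.016 in place of 18, the results are 250 / 18.016 = 13.88 and 13.2 × 18.016 = 237.8, so the conclusion does not change.

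**Step 3. Could rounding or a loose factor explain it?**

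The loosest glucose pair in the document is 95 mg/dL with 5.2 mmol/L in Section 3.1 (Section 3.3.2 has 5.3). It implies 95 / 5.2 = 18.27. Even that factor gives 250 / 18.27 = 13.7 mmol/L, still 0.5 above the stated figure. Rounding to one decimal moves a value by at most 0.05.

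**Step 4. Size of the gap**

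- 13.89 − 13.2 = 0.69 mmol/L.
- 250 − 237.6 = 12.4 mg/dL, and 12.4 / 250 = 5.0% of the limit.
- Discordant range: about 238 to below 250 mg/dL. In SI results reported to one decimal this is 13.2 to 13.8 mmol/L, because 13.8 × 18 = 248.4 is below 250 and 13.9 × 18 = 250.2 is above it.

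**Step 5. Is the rest of the table sound?**

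Using standard conversion factors, creatinine 2.5 mg/dL gives 221 µmol/L (stated 221), cholesterol 350 mg/dL gives 9.05 mmol/L (stated 9.1), and BUN 40 mg/dL gives 14.28 mmol/L (stated 14.2). These agree exactly or to within 0.1. Among these rows, the upper FPG pair is the only one that clearly fails.

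**The case against.** The arithmetic is hard to dispute. The case on the other side concerns how far it reaches, and most of that case stands.

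**A reader might infer that the main safety assessment is affected.** Section 6.1.6 says that safety will rest mainly on adverse events and on "the number of laboratory values that fall outside of pre-determined ranges". But nothing there equates those ranges with Appendix 3. The same section says that shift tables use extended normal ranges, and that raw values and changes are summarised directly. Only the listing flags are tied to notable values. The supported consequences are the CRF comment and the listing flag.

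**A reader might infer that flags will in fact differ between sites or countries.** This is possible in a trial across about 39 countries that allows local laboratories where needed. It is not shown. Section 3.5.4 sends samples to a central laboratory by default and calls for standardised ranges and common methods, and Section 5.2 has results sent electronically. If the flags are programmed in one unit, they will be consistent across patients, and the open question is which cut-off they apply.

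**A reader might size the problem by the number of patients expected to progress to diabetes.** That counts the wrong thing. Progression is defined at 126 mg/dL fasting or 200 mg/dL two hours after challenge, so most of that count says nothing about an FPG between 238 and 250 mg/dL. The 6% annual rate in Section 6.2 is also a placebo assumption. The document gives no FPG distribution, so no count of affected values can be derived.

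It is also fair to say that the stored FPG values are unaffected whichever flag is applied. None of this removes the contradiction. A threshold that imposes a duty on investigators is printed as two different thresholds.

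**Conclusion.** The point holds, and it is minor. The two upper notable FPG limits in Appendix 3 differ by about 0.7 mmol/L (12 mg/dL, 5%). Values from about 238 to below 250 mg/dL are notable under one column and not under the other. For those values, the requirement for a CRF comment and the listing flag depend on the column applied.

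The conclusion rests only on the glucose conversion factor, which the protocol's own pairs fix at about 18. It does not depend on any assumption about the patients.

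The error stops there. The diabetes endpoint, eligibility, titration criteria, the rule on when an annual OGTT is no longer required, alpha and sample size do not use this limit. The number of values in the gap is unknown. Only the protocol is at hand, so how the flags are programmed cannot be checked.

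**What to change.** Reconcile the two upper FPG figures in Appendix 3 so that both columns express one limit. The document does not show which was intended, so the sponsor has to settle this. Then check the flag programming against the reconciled limit and re-derive the listing flags from the stored FPG values.

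The cost is one corrected figure, which can travel with the next protocol amendment (Section 8.2.1 requires changes to be made that way), and a short programming check. Listing flags can be rebuilt at any time. Investigator comments that were not made when the result arrived are harder to recover, which favours making the correction early.
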